1 FLOW CHARTS

1.1 GRAPHICAL STUDY DESIGN (MAIN PHASE)

1.1.1 COHORTS 1 TO 3

[figure not shown]
1.1.2 COHORT 4

- * Inclusion (I): The inclusion or entry into the open-label dose finding treatment period for Cohort 4.
- ** The main phase for Cohort 4 will include 3 alirocumab injections (at W0, W4, and W8).
- *** For Cohort 4, the study duration includes an extended 12 week treatment period, including a Week 10 visit, but will not have a follow up period, in contrast to the study design for Cohorts 1, 2, and 3.
- **** Week 12 is the end of the open-label dose finding treatment period and possible entry point into the extension for Cohort 4.

[figure not shown]
1.2 GRAPHICAL STUDY DESIGN (OPTIONAL EXTENSION PHASE)

1.2.1 COHORTS 1 TO 3

1.2.2 COHORT 4

OPEN-LABEL EXTENSION (OLE) PERIOD

- * All patients enrolled in Cohort 4 who successfully complete the main phase will be offered entry into the extension phase at Week 12 or directly switch to the phase 3 study (EFC14643).
- ** Visits will continue until at least 6 weeks (corresponding to the wash out period of 10 weeks after the last alirocumab injection) before the initiation of the pediatric Phase 3 study in which the site where the patient is potentially participating where the latest end date for Cohort 4 will be December 2018.
- *** A follow-up phone call will take place at least 10 weeks after the last IMP for all cohorts, except those patients who refuse phase 3.
- **** The Q4W dose for Cohort 4 administered during the open label-dose finding treatment period of the main phase will initially be continued in the extension phase.

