ASSESSMENT SCHEDULE	
MAIN PHASE
 
Screening period:
 
The screening period is up to 6 weeks (+ 1 week), with 1 to 2 visits that are anticipated, depending on the duration of stable LMT dosing and the need for mandatory heFH genetic testing.
 
Patients can be enrolled during this period as soon as eligibility is confirmed.
 
Open-label dose finding treatment period:
 
For Cohorts 1 to 3, visits schedule from entry into the open-label dose finding treatment period: baseline Visit (V2, Week 0) and then every 2 weeks (ie, Weeks 2, 4, 6) until the end of the open-label dose finding period (Week 8). The visits at Week 2 and Week 6 will take place either at the clinical site or patient's home, depending upon local arrangements and preferences of the investigator/patient.
 
For Cohort 4, visits schedule from entry into the open-label dose finding treatment period: baseline, Visit (V2, Week 0), and then every 4 weeks (ie, Weeks 0, 4, and 8) until the end of the open-label dose finding period (Week 12) will take place at the clinical site. Visits at Week 2 and Week 6 will be a phone call and at Week 10 will be at the clinical site.
 
Follow-up period, only for Cohort 1 to Cohort 3:
 
Follow-up visits will take place 6 and 10 weeks after the last alirocumab injection administered during the open-label dose-finding treatment period. This corresponds to Week 12 and Week 16 for Cohorts 1 & 2 or Week 10 and Week 14 for Cohort 3. The Week 10 or Week 12 visit will be conducted through a phone call if there is no safety concern by the investigator.
 
EXTENSION PHASE
 
Open-label extension (OLE) period:
 
After successful completion of Week 16 visit for Cohorts 1 & 2 or Week 14 visit for Cohort 3, patients will be offered entry into an optional OLE period. The first visit of the OLE period will overlap with the final follow-up visit of the main phase. Visits will take place at Week 20, Week 24, Week 28 and then every 12 weeks thereafter for assessments for Cohorts 1 & 2. Visits will take place at Week 18, Week 22, Week 26 and then every 12 weeks thereafter for assessments for Cohort 3. Depending on the clinical supplies and/or alternative contingency plans, more frequent visits such as every 2 weeks (for Cohorts 1 & 2) or every 4 weeks (for Cohort 3) may be required. Visits will continue until visit end of OLE at least 2 or 4 weeks after last alirocumab injection (with a follow-up phone call at least 10 weeks after the last alirocumab administration) before the initiation of the pediatric Phase 3 study in the site where the patient is potentially participating or December 2018, whichever comes first. A follow-up phone call will take place at least 10 weeks after the last IMP of each cohort.
 
All patients enrolled in Cohort 4 who successfully complete the open-label dose-finding treatment period will also be offered either entry into the extension phase at

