The addition to the higher doses in the Q4W cohort with extended 12 week study duration (including 2 new visits at Week 10 and Week 12) for the open label dose-finding period will more appropriately ensure that steady state has been reached after 3 alirocumab injections (2 interdose intervals) in terms of PK and LDL-C and related parameter reduction efficacy. An intermediate visit between the dosing interval (Week 10) is specifically introduced to better document the PK and LDL-C data from the Q4W dosing regimen that is known to show some peak-trough variability over the 4-week dosing interval, ie, a peak in the decrease at the mid dosing interval time point and trough reduction in LDL-C at the end of dosing interval time period. Thus, extending the duration of a higher Q4W dosing regimen to 12 weeks (an additional 4 weeks) will secure more comprehensively data on the LDL-C related profile reduction potential of a Q4W dosing regimen for alirocumab.

Given the 12 week duration, only LDL-C and key related parameters (TC, non-HDL-C, and TG) will be measured at Week 10 and Week 12 to minimize blood collection. The post-treatment follow-up period is no longer needed based on the data collected from the previous 3 cohorts.

All patients in Cohort 4 will receive alirocumab at 150 mg Q4W for BW <50 mg/300 mg Q4W for BW \geq 50 kg using prefilled syringes.

Cohort 4, similar to the other cohorts, will include alirocumab administration during the open-label extension that will continue until approximately 10 weeks before the initiation of the pediatric phase 3 study or December 2018 at the latest. The patients, after a wash-out period of at least 10 weeks after the last injection of alirocumab, will have the opportunity to participate in the phase 3 study. Though Cohorts 1 to 3 will be switched to the optimal regimen selected for the phase 3 study, Cohort 4 will remain on their initial regimen given the planned study end date of December 2018.

Conclusion on the benefit risk assessment with alirocumab:

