6.2 DURATION OF STUDY PARTICIPATION

6.2.1 Duration of study participation for each patient

Main open-label treatment phase:

For Cohorts 1 to 3, a study duration of approximately 16-23 weeks (screening/run in period: up to 6 [+1] weeks, main open-label treatment period: 8 weeks, follow-up period: 6-8 weeks)

For Cohort 4, a study duration of approximately 14-19 weeks (screening period: up to 6 [+1] weeks, open-label dose-finding treatment period: 12 weeks).

Open-label extension phase:

Patients who enroll in the open-label extension treatment period will continue alirocumab administration until at least 10 weeks before the initiation of the pediatric Phase 3 study in the site where the patient is potentially participating. Therefore, patients who consent to participate in the pediatric phase 3 study could have their last alirocumab injection in the OLE period up to December 2018, depending on timing of site initiation for the phase 3 study planned to be done no later than December 2018. All other patients, enrolled in the OLE period, who decline the participation in the phase 3 study, will have their last alirocumab injection on December 2018. This corresponds to a maximum of approximately 24 months for the first patients enrolled in Cohorts 1 to 3. For Cohort 4, this corresponds to a maximum of approximately 7 months for the first patients enrolled.

For both phases, patients who experience an ongoing Serious Adverse Event (SAE) or an Adverse Event of Special Interest (AESI), at the pre-specified study end-date, should be followed until resolution, stabilization, or death and related data will be collected.

End of study per patient:

If patient does not participate to the open label extension period, then the end of the study is the last on site visit as scheduled by protocol (ie, visit Week 14 or Week 12 (Cohorts 3 & 4, respectively) or Week 16 (Cohorts 1 & 2) or the resolution/stabilization of all SAEs, and AESI, whatever comes last.

If patient participates in the open label extension period, then the end of the study is the last on site visit as scheduled by protocol (ie, visits will continue until visit end of OLE at least 2 or 4 weeks after last alirocumab injection (with a follow-up phone call at least 10 weeks after the last alirocumab administration) before the initiation of the pediatric Phase 3 study in the site where the

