patient is potentially participating or December 2018, at the latest, or the resolution/stabilization of all SAEs, and AESI, whatever comes last.

A follow-up phone contact will take place at least 10 weeks after the last IMP of each cohort, including Cohort 4.

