9.2.3 Safety endpoints

The safety endpoints will be adverse events, serious adverse events, adverse events of special interest, laboratory data, vital signs, Tanner stage assessment, body weight, and height assessed throughout the study.

9.2.3.1 *Observation period*

The observation of safety data will be as follows:

- Pretreatment period: The Pretreatment observation period is defined from the signed informed consent up to the first dose of IMP.
- Treatment emergent adverse event (TEAE) period: The TEAE observation period is defined as the time from the first dose of IMP to the last dose of IMP injection +70 days

(10 weeks) as residual effect of alirocumab is possible until 10 weeks after the stop of treatment IMP injection.

- Post-treatment period: The post-treatment observation period is defined as the time starting the day after the end of the TEAE period up to the end of the study (see definition in [Section 6.2.2](#)).

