 - Gonadal and pituitary hormones: testosterone (male) and estradiol (female), luteinizing hormone (LH), follicle-stimulating hormone (FSH),
 - Fat soluble vitamins: retinol (vitamin A), 25hydroxy-vitamin D (vitamin D), alpha-tocopherol (vitamin E), phylloquinone (vitamin K),
 - CPK,
 - Anti-alirocumab antibodies.

10.1.4.7 Follow-up Phone contact at least 10 weeks after the last IMP injection for all cohorts

- Collect AEs if any.
- Record concomitant medication.
- In case of clinically relevant abnormality not recovered at the end of OLE visit, plan an unscheduled visit & perform physical examination/ laboratory examinations if needed.

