For Cohorts 1- 3, the initial dose of alirocumab that will be administered during the extension phase, will be the continuation of same doses/regimens administered during the main phase up to the time when the final optimal doses for the Phase 3 study are selected and prefilled syringes

available. Then these final optimal doses will be administered to all patients during the extension phase, based on their body weight at the time of dose change.

For Cohort 4, if patients enter the OLE phase, patients will continue on their doses from the main phase.

At the end of each study phase, patients are to be followed 10 weeks after last alirocumab injection on site (for main phase, only for Cohorts 1-3 as this follow up period doesn't apply for Cohort 4) or by phone (for extension phase, for all cohorts). Patients with any adverse event (AE) should be followed until resolution, stabilization, or death, as specified in the protocol.

Approximately 40 patients (10 patients per cohort) were to be enrolled from approximately 28 sites.

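### The protocol contradicts itself on whether extension patients who decline Phase 3 get the 10-week safety call, and on what December 2018 marks; if the call is skipped, the SAP still counts the uncontacted days as event-free

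*Protocol*

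**What the plan says.** **The call.** The footnote to the Cohort 4 extension diagram (Protocol 1.2.2) places a call at least 10 weeks after the last dose "for all cohorts, except those patients who refuse phase 3". Elsewhere there is no exception:

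- Synopsis, assessment schedule: "A follow-up phone call will take place at least 10 weeks after the last IMP of each cohort".
- Protocol 6.2.1: "A follow-up phone contact will take place at least 10 weeks after the last IMP of each cohort, including Cohort 4".
- Protocol 10.1.4.7, section title: "Follow-up Phone contact at least 10 weeks after the last IMP injection for all cohorts".
- Protocol 1.4.1 and 1.4.2: each flow chart has a column for the call. In the Cohort 4 chart it has its own visit number, a window and an adverse event mark.
- SAP 1.1: the 10-week follow-up is done "by phone (for extension phase, for all cohorts".

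**The dates.** Patients in the extension who decline Phase 3 "will have their last alirocumab injection on December 2018" (Protocol 6.2.1; the synopsis agrees). The synopsis and 6.2.1 bound extension visits by the start of Phase 3 at the site or December 2018. Protocol 4 keeps Cohort 4 on its starting regimen "given the planned study end date of December 2018", and 6.1 and 10.1.4 repeat that reason.

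**The safety window.** Protocol 9.2.3.1 sets the treatment-emergent window at 70 days after the last dose, "as residual effect of alirocumab is possible until 10 weeks after the stop of treatment IMP injection". SAP 2.1.4 uses the same 70 days after the last extension injection. Under SAP 2.4.5.1, a patient without an event contributes the full length of that period to patient-years and is censored at its end in the Kaplan-Meier curves. SAP 2.2 reports as insufficiently followed any patient with no call or on-site visit more than 9 weeks after the last injection.

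**The concern.** A site working from the Cohort 4 diagram could reasonably skip the call for a patient who refuses Phase 3. Those patients have no later study contact planned, whereas Phase 3 entrants would be seen again. Protocol 10.3.4 asks for at least 10 weeks of follow-up after premature discontinuation in either period. With the footnote applied, a decliner who completes the extension would therefore be followed for less time than one who stops early.

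Adverse events are at stake, and so are pregnancies, which are events of special interest; 8.8.2 requires contraception for the same 10 weeks. In the analysis, days on which no contact was scheduled would enter the denominator as event-free time. That pulls patient-year rates and Kaplan-Meier estimates downward.

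**Working it through.** **Inputs.** Treatment-emergent window: 70 days after last injection (Protocol 9.2.3.1, SAP 2.1.4). End-of-extension visit: at least 14 days (Q2W) or 28 days (Q4W) after last injection, with a 7-day window (Protocol 1.4.1, 1.4.2). Decliners' last injection: 1 to 31 December 2018 (synopsis, 6.2.1).

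**The plan's own figures.** 10 weeks × 7 = 70 days. 10 − 4 = 6 weeks, the interval in Protocol 1.2.2 between the last Q4W visit and the end of washout. Both reproduce.

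**Days without scheduled contact if the footnote governs.** Uncovered = 70 − day of last scheduled contact.

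| Regimen | Last contact | Uncovered days | Share of 70 |
|---|---|---|---|
| Q2W | day 14 | 56 | 80% |
| Q2W, visit 7 days later | day 21 | 49 | 70% |
| Q4W | day 28 | 42 | 60% |
| Q4W, visit 7 days later | day 35 | 35 | 50% |

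If the unconditional passages govern, a contact occurs at day 70 or later and the uncovered count is 0.

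**Where the call falls.** Call date = last injection + 70 days. 1 December 2018 + 70 = 9 February 2019; 31 December 2018 + 70 = 11 March 2019. That is 40 to 70 days after 31 December.

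**Where the end-of-extension visit falls.** For Q4W, 31 December − 28 days = 3 December, so any later injection puts the visit into 2019. For Q2W, 31 December − 14 days = 17 December.

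**If contact stopped on 31 December 2018.** Uncovered share = (70 − days from injection to 31 December) / 70. Injection on 1 December: 40/70 = 57%; 15 December: 54/70 = 77%; 31 December: 70/70 = 100%.

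**Share of one patient's total person-time (illustration).** Take the first Cohort 4 patient, with enrolment planned for 1 May 2018 (SAP 1.5), and assume a last injection on 1 December 2018. The time from first to last injection is 214 days, so the treatment-emergent period is 214 + 70 = 284 days and the gap is 42/284 = 15%. For an early Q2W patient, assume about 24 months (730 days) to the last injection: 56/(730 + 70) = 7%. Later enrolees have shorter treatment and a larger share.

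**The case against.** A reader might infer that most of every decliner's 70-day window has no contact. The documents do not support that. It needs one diagram footnote, or a hard December 2018 cut-off, to override at least six places that schedule the call, including Cohort 4's own flow chart. The diagram is not shown, so where the footnote mark attaches cannot be checked.

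A reader might also infer that the study closes for these patients at the last on-site visit, after which Protocol 10.4.4 asks only for serious events judged related. But the same sentence in 6.2.1 mentions the 10-week call and runs on to resolution of serious events and events of special interest, whichever is last. Protocol 6.2.2 ends the trial at the last visit or contact, with no calendar date. Protocol 10.4.3 collects adverse events to the post-treatment follow-up visit. A call in 2019 is therefore not excluded.

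The planned study end is worded for Cohort 4, as a reason not to change regimen. No passage requires the call by 31 December, so working back to a date by which dosing should have ended would test a constraint that the plan does not contain.

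SAP 2.2 does make under-followed patients visible. The 60 to 80% is a share of the post-dose tail, not of the rate denominator.

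All of this stands, and it makes the gap conditional. It does not remove the contradiction about the call or the loose use of December 2018. Nor does SAP 2.2 shorten anyone's person-time.

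**Conclusion.** This is an internal inconsistency of minor to moderate severity. The passages disagree on whether decliners get the 10-week call. The December 2018 statements do not fit together once a December injection is followed by a visit 14 or 28 days later and a call 70 days later.

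The size is conditional. With the footnote applied and the end-of-extension visit at its earliest day, 42 (Q4W) or 56 (Q2W) of 70 days per affected patient have no scheduled contact. With the unconditional passages applied, none do. The number who decline Phase 3 is not stated, so the effect on overall adverse event rates cannot be estimated. The 7% and 15% person-time figures are illustrations that rest on the assumed injection dates.

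**What to change.** 1. **Protocol, the call.** Reconcile the 1.2.2 footnote with the synopsis, 1.4.1, 1.4.2, 6.2.1, 10.1.4.7 and SAP 1.1, so that one rule on the call for decliners appears throughout.
2. **Protocol, the dates.** Reconcile the December 2018 statements on last injection, last extension visit and planned study end with each other. Reconcile the last-on-site-visit wording for end of study in 6.2.1 with the 10-week contact. This point proposes no last-dose date.
3. **SAP 2.1.4 and 2.4.5.1.** For an event-free patient with no contact at or after day 70, end combined treatment-emergent person-time and Kaplan-Meier censoring at the last contact. SAP 3 already truncates this period at the cut-off date for ongoing patients, so the device is not new. Show the SAP 2.2 count of insufficiently followed patients beside the incidence tables, because person-time truncation does not change crude percentages.

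The cost is a clarification to the protocol, one censoring rule in the SAP and, where the call is kept, one call per decliner that is already scheduled elsewhere. If sites had treated 31 December 2018 as the close, the last contact would move by up to 70 days.

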1.3 STUDY FLOWCHART (MAIN PHASE)

1.3.1 COHORTS 1 TO 3

Main Phase Cohorts 1 to 3	Screening Period (including run-in if applicable)	Open-Label Dose Finding Treatment Period						Follow-Up Period	
		2	3	4	5	6	7		
VISIT	1 ^c	2	3	4	5	6	7	8	
Week (W)	Up to W-6	W0/D1	W2	W4	W6	W8	W10 (Cohort 3) or W12 (Cohorts 1 & 2)	W14 (Cohort 3) or W16 (Cohorts 1 & 2)	
Visit Window (+/- days)	+7		±3	±3	±3	±3	±7	±7	
Visit Type	Clinical Site	Clinical Site	Clinical Site or Patient's Home ^a	Clinical Site	Clinical Site or Patient's Home ^a	Clinical Site	Clinical site or Phone Call ^a	Clinical Site	
Informed Consent	X								
heFH Genotyping Informed Consent (if needed)	X								
Inclusion Criteria	X	X							
Exclusion Criteria	X	X							
Patient Demography	X								
Medical/Surgical/ Family medical History	X								
Alcohol/Smoking habits	X								
Prior Medication History ^r	X								
Physical Examination	X	X					X	X ^d	X ^d

Main Phase Cohorts 1 to 3	Screening Period (including run-in if applicable)	Open-Label Dose Finding Treatment Period						Follow-Up Period	
		2	3	4	5	6	7		
VISIT	1 ^c	2	3	4	5	6	7	8	
Week (W)	Up to W-6	W0/D1	W2	W4	W6	W8	W10 (Cohort 3) or W12 (Cohorts 1 & 2)	W14 (Cohort 3) or W16 (Cohorts 1 & 2)	
Visit Window (+/- days)	+7		±3	±3	±3	±3	±7	±7	
Visit Type	Clinical Site	Clinical Site	Clinical Site or Patient's Home ^a	Clinical Site	Clinical Site or Patient's Home ^a	Clinical Site	Clinical site or Phone Call ^a	Clinical Site	
Measured Body Weight	X	X		X		X		X	
Measured Height	X							X	
Tanner Stages ^b	X							X	
IVRS/IWRS contact	X	X	X	X	X			X	
Inclusion		X							
Treatment:									
Alirocumab Administration Q2W (Cohorts 1 & 2) ^e		X	X	X	X				
Alirocumab Administration Q4W (Cohort 3 only) ^e		X		X					
Concomitant Medication	X	X	X	X	X	X	X	X	
Review of diet ^s	X	X		X		X			
Check of stability of background LMT	X	X	X	X	X	X			

Main Phase Cohorts 1 to 3	Screening Period (including run-in if applicable)	Open-Label Dose Finding Treatment Period						Follow-Up Period	
		2	3	4	5	6	7		
VISIT	1 ^c	2	3	4	5	6	7	8	
Week (W)	Up to W-6	W0/D1	W2	W4	W6	W8	W10 (Cohort 3) or W12 (Cohorts 1 & 2)	W14 (Cohort 3) or W16 (Cohorts 1 & 2)	
Visit Window (+/- days)	+7		±3	±3	±3	±3	±7	±7	
Visit Type	Clinical Site	Clinical Site	Clinical Site or Patient's Home ^a	Clinical Site	Clinical Site or Patient's Home ^a	Clinical Site	Clinical site or Phone Call ^a	Clinical Site	
Efficacy:									
Total-C, calculated LDL-C, HDL-C, TG, non-HDL-C ^f	X	X		X		X			
Apo B, Apo A-1, ratio Apo B / Apo A-1, and Lp(a) ^f	X	X				X			
Safety:									
AE /SAE recording (if any)	X	X	X	X	X	X	X	X	
Vital Signs ^t	X	X		X		X			X

	Screening Period (including run-in if applicable)	Open-Label Dose Finding Treatment Period						Follow-Up Period	
		2	3	4	5	6	7	8	
VISIT	1 ^c	2	3	4	5	6	7	8	
Week (W)	Up to W-6	W0/D1	W2	W4	W6	W8	W10 (Cohort 3) or W12 (Cohorts 1 & 2)	W14 (Cohort 3) or W16 (Cohorts 1 & 2)	
Visit Window (+/- days)	+7		±3	±3	±3	±3	±7	±7	
Visit Type	Clinical Site	Clinical Site	Clinical Site or Patient's Home ^a	Clinical Site	Clinical Site or Patient's Home ^a	Clinical Site	Clinical site or Phone Call ^b	Clinical Site	
Laboratory Testing^f:									
heFH genotyping (Mandatory for consenting patients without documented heFH diagnosis; optional for documented heFH diagnosis patients wishing to undergo genotyping) ^g	X	X	X	X	X	X			
Hematology and chemistry ^h	X			X		X		X ^q	
Creatine phosphokinase (CPK)	X			X		X		X ^q	
Liver panel ⁱ	X			X		X		X ^q	
Adrenal gland hormones ^j		X				X			
Gonadal and pituitary hormones ^k		X				X			
Fat soluble vitamins ^l		X				X			
Pregnancy test ^m	X	X				X		X	
Anti-alirocumab antibodies (ADA) ^{n o}		X				X		X ^o	
PCSK9 levels (free and total)/serum alirocumab concentration (PK) ⁿ		X		X		X		X	

- a The Week 2 and Week 6 visits will take place either at the clinical site or patient's home, depending upon local arrangements and preferences of the Investigator/patient. For Cohort 3, a phone call may be done instead of a home or office visit.
- b The Week 10 or Week 12 visit will be conducted at clinical site or through a phone call if no safety concerns by the investigator
- c Two site visits may be needed to complete eligibility confirmation.
- d Physical examination at the follow-up visits should be performed only in case of clinically relevant abnormality at Week 8 visit.
- e Alirocumab injections will be prepared from vials by the pharmacist (or equivalent). For Cohorts 1 & 2 the Weeks 0 and 4 alirocumab injections will be administered at the clinical site by the site staff. The Weeks 2 and 6 alirocumab injections will be administered at the clinical site by the site staff or at the patient's home by a health care professional, depending upon local arrangements and preferences of the Investigator/patient. For Cohort 3 the Weeks 0 and 4 alirocumab injections will be administered at the clinical site by the site staff, the Week 2 and Week 6 visits could be done at the patient's home by a health care professional but without injections. Prior to each alirocumab administration, a local topical anesthetic may be utilized as per the Investigator.
- f Prior to any laboratory testing, the site may utilize a local topical anesthetic as per the Investigator. In case only a limited amount of blood can be drawn, specific tests performed for each sample obtained will be prioritized.
- g Genotyping for heFH will be conducted from a specimen of whole blood, saliva, or buccal swab in patients consenting to undergo genotyping testing. This test will be recommended for all patients but will be mandatory only for patients without clinical diagnosis or no previous documented genotyping. In case of non-mandatory genotyping the sample could be taken preferentially during the screening period but could be done at any visit during the 8-week dose-finding part of the trial.
- h Hematology includes: complete blood cell count (CBC) including hematocrit, hemoglobin, red blood cell count, white blood cell count with differential count, and platelets. Chemistry includes: glucose, sodium, potassium, chloride, bicarbonate, calcium, phosphorous, urea nitrogen, creatinine, uric acid, lactate dehydrogenase (LDH), total protein, albumin, and γGT.
- i Liver panel: ALT, AST, alkaline phosphatase (ALP), and total bilirubin.
- j Adrenal gland hormones: cortisol (with reflexive ACTH levels if cortisol <LLN) and dehydroepiandrosterone sulfate (DHEAS).
- k Pituitary hormones: luteinizing hormone (LH) and follicle-stimulating hormone (FSH). Gonadal hormones: testosterone [males] and estradiol [females].
- l Fat soluble vitamins: A (retinol), D (25 hydroxy vitamin D), E (alpha-tocopherol), and K (phylloquinone).
- m Pregnancy test should be done on females of childbearing potential who are sexually active or females who have experienced menarche. The Screening (Week -2) pregnancy test should be a blood test. All other pregnancy tests will be with a local urine pregnancy test.
- n ADA and PK samples should be collected before alirocumab administration.
- o Only patients who prematurely discontinue the main phase or do not enter the optional extension phase and have a titer at or above 240 for ADA at follow-up visit will have additional ADA samples, at 6 to 12 months after the last alirocumab administration and thereafter, about every 3 to 6 months until titer returns below 240.
- p See [Appendix E](#) for Tanner stages evaluation.
- q Only in case of clinically relevant abnormal values at the end of the treatment visit (Week 8).
- r Document prior medication history within the previous 12 weeks, especially for lipid modifying therapy (including statin) and nutraceutical products that may affect lipids (eg, omega-3 fatty acids, plant stanols such as found in Benecol, flax seed oil, psyllium).
- s Patients will be instructed to follow a diet in accordance with the American Academy of Pediatrics guidelines or equivalent throughout the entire study.
- t Vital signs include: heart rate, systolic and diastolic BP in sitting position.

1.3.2 COHORT 4

Main Phase Cohort 4	Screening Period (including run-in if applicable)	Open-Label Dose-finding Treatment Period							
		1	2	3	4	5	6	7	8
VISIT		1	2	3	4	5	6	7	8
Week (W)	Up to W-6	W0/D1 ^b	W2	W4	W6	W8	W10	W12	
Visit Window (+/- days)	+7		±3	±3	±3	±3	±7	±7	
Visit Type	Clinical Site	Clinical Site	Phone Call	Clinical Site	Phone Call	Clinical Site	Clinical site ^a	Clinical Site	
Informed Consent	X								
heFH Genotyping Informed Consent (if needed)	X								
Inclusion Criteria	X	X							
Exclusion Criteria	X	X							
Patient Demography	X								
Medical/Surgical/ Family medical History	X								
Alcohol/Smoking habits	X								
Prior Medication History ^o	X								
Physical Examination	X	X				X			
Measured Body Weight	X	X		X		X		X	
Measured Height	X							X	
Tanner Stages ⁿ	X							X	
IVRS/IWRS contact	X	X						X	
Inclusion		X							

Main Phase Cohort 4	Screening Period (including run-in if applicable)	Open-Label Dose-finding Treatment Period							
		1	2	3	4	5	6	7	8
VISIT		1	2	3	4	5	6	7	8
Week (W)		Up to W-6	W0/D1 ^b	W2	W4	W6	W8	W10	W12
Visit Window (+/- days)		+7		±3	±3	±3	±3	±7	±7
Visit Type		Clinical Site	Clinical Site	Phone Call	Clinical Site	Phone Call	Clinical Site	Clinical site ^a	Clinical Site
Treatment:									
Alirocumab Administration Q4W ^c			X		X		X		
Concomitant Medication		X	X	X	X	X	X	X	X
Review of diet ^d		X	X		X		X		X
Check of stability of background LMT		X	X	X	X	X	X		X
Efficacy:									
Total-C, calculated LDL-C, HDL-C, TG, non-HDL-C ^d		X	X		X		X	X	X
Apo B, Apo A-1, ratio Apo B / Apo A-1, and Lp(a) ^d		X	X				X		
Safety:									
AE /SAE recording (if any)		X	X	X	X	X	X	X	X
Vital Signs ^g		X	X		X		X		X

Main Phase Cohort 4	Screening Period (including run-in if applicable)	Open-Label Dose-finding Treatment Period							
		1	2	3	4	5	6	7	8
VISIT		1	2	3	4	5	6	7	8
Week (W)	Up to W-6	W0/D1 ^b	W2	W4	W6	W8	W10	W12	
Visit Window (+/- days)	+7		±3	±3	±3	±3	±7	±7	
Visit Type	Clinical Site	Clinical Site	Phone Call	Clinical Site	Phone Call	Clinical Site	Clinical Site ^a	Clinical Site	
Laboratory Testing ^d :									
heFH genotyping (Mandatory for consenting patients without documented heFH diagnosis; optional for documented heFH diagnosis patients wishing to undergo genotyping) ^e	X	X		X		X			
Hematology and chemistry ^f	X			X		X			
Creatine phosphokinase (CPK)	X			X		X			
Liver panel ^g	X			X		X			
Adrenal gland hormones ^h		X				X			
Gonadal and pituitary hormones ⁱ		X				X			
Fat soluble vitamins ^j		X				X			
Pregnancy test ^k	X	X				X			X
Anti-alirocumab antibodies (ADA) ^{l/m}		X				X			
PCSK9 levels (free and total)/serum alirocumab concentration (PK) ^l		X		X		X	X	X	X

a The Week 0, 4, 8, 10 and 12 visits will take place at the clinical site. For Week 2 and Week 6, a phone call may be done instead of a home or office visit.

b Two site visits may be needed to complete eligibility confirmation.

c The Week 0, 4 and 8 alirocumab injections will be administered at the clinical site by the site staff. Prior to each alirocumab administration, a local topical anesthetic may be utilized as per the Investigator, if at clinical site

- d Prior to any laboratory testing, the site may utilize a local topical anesthetic as per the Investigator. In case only a limited amount of blood can be drawn, specific tests performed for each sample obtained will be prioritized.
- e Genotyping for heFH will be conducted from a specimen of whole blood, saliva, or buccal swab in patients consenting to undergo genotyping testing. This test will be recommended for all patients but will be mandatory only for patients without clinical diagnosis or no previous documented genotyping. In case of non-mandatory genotyping the sample could be taken preferentially during the screening period but could be done at any visit during the 8-week dose-finding part of the trial.
- f Hematology includes: complete blood cell count (CBC) including hematocrit, hemoglobin, red blood cell count, white blood cell count with differential count, and platelets. Chemistry includes: glucose, sodium, potassium, chloride, bicarbonate, calcium, phosphorous, urea nitrogen, creatinine, uric acid, lactate dehydrogenase (LDH), total protein, albumin, and γGT.
- g Liver panel: ALT, AST, alkaline phosphatase (ALP), and total bilirubin.
- h Adrenal gland hormones: cortisol (with reflexive ACTH levels if cortisol <LLN) and dehydroepiandrosterone sulfate (DHEAS).
- i Pituitary hormones: luteinizing hormone (LH) and follicle-stimulating hormone (FSH). Gonadal hormones: testosterone [males] and estradiol [females].
- j Fat soluble vitamins: A (retinol), D (25 hydroxy vitamin D), E (alpha-tocopherol), and K (phylloquinone).
- k Pregnancy test should be done on females of childbearing potential who are sexually active or females who have experienced menarche. The Screening (Week -2) pregnancy test should be a blood test. All other pregnancy tests will be with a local urine pregnancy test.
- l ADA and PK samples should be collected before alirocumab administration.
- m Only patients who prematurely discontinue the main phase or do not enter the optional extension phase and have a titer at or above 240 for ADA at follow-up visit will have additional ADA samples, at 6 to 12 months after the last alirocumab administration and thereafter, about every 3 to 6 months until titer returns below 240.
- n See [Appendix E](#) for Tanner stages evaluation.
- o Document prior medication history within the previous 12 weeks, especially for lipid modifying therapy (including statin) and nutraceutical products that may affect lipids (eg, omega-3 fatty acids, plant stanols such as found in Benecol, flax seed oil, psyllium).
- p Patients will be instructed to follow a diet in accordance with the American Academy of Pediatrics guidelines or equivalent throughout the entire study.
- q Vital signs include: heart rate, systolic and diastolic BP in sitting position.

